#### 10.6 Reporting Procedures – Participating Investigators

As the study intervention and data collection will be conducted only at NYU, procedures for monitoring and reporting across sites are not provided.

#### 10.7 Study Halting Rules

As this study is minimal risk, it is not anticipated that the study may be halted. However, if there is a determination of unexpected, significant, or unacceptable risk to participants, the study may be temporarily suspended or prematurely terminated as described in section 6.7.

#### 10.8 Safety Oversight

It is the responsibility of the Principal Investigator to oversee the safety of the study at his/her site. This safety monitoring will include careful assessment and appropriate reporting of adverse events as noted above, as well as the construction and implementation of a site data and safety-monitoring plan. Medical monitoring will include a regular assessment of the number and type of serious adverse events.

Version Date: September 27, 2019

Following are plans for data and safety monitoring during the pilot study.

Monitoring entity. This study will be monitored by the PI, the research coordinator, the bio-statistician, and the IRB. The PI will ensure that the research coordinator and statistician undergo training in the study protocol. The research coordinator will also be trained in the safety protocol for depression. The PI will oversee adherence to the study protocol to ensure the safety, reliability, and validity of data collection. The PI will be responsible for submitting all necessary reports to the study sponsor and the IRB. The research coordinator will prepare weekly reports on participant demographics, recruitment, attrition, data collection, data entry updates, and any other issues or concerns since the last research team meeting. The statistician will prepare monthly reports about missing, invalid, or inconsistent data on selected key variables. The reports will also contain a summary of monthly accrual and cumulative accrual, a summary of key characteristics of the study participants, and a summary of the completeness and quality of data.

**Monitoring Study Safety.** Once enrollment is initiated, the PI will arrange weekly meetings. These meetings will consist of retrospective and concurrent evaluation of all research procedures, including participant screening for inclusion/exclusion criteria, the informed consent process, and participant study instructions, as well as any necessary staff training in the IRB approved study protocol. Participant demographics, recruitment, retention, data collection, and data entry updates will be monitored weekly.

Quality control assurances of data will be reviewed in monthly meetings and will include information about missing, invalid, inconsistent data on selected key variables, and a summary of key characteristics of the study participants. A random sample of participants' research records will be reviewed to ensure compliance with IRB requirements, conformance with informed consent requirements, verification of source documents, and investigator compliance by the PI monthly. Meetings will also be arranged by the PI if an adverse event occurs.

**Minimizing research-associated risk.** We do not believe that there are any major risks associated with the proposed study, although a subject may be identified with moderate/severe or severe depression. This is not a research-associated risks but may be detected during screening or participation in the study. The sleep intervention and accelerometry monitoring have minimal risk. Trained research personnel will perform all testing and will be monitored by the PI. Throughout the study, the PI and the research coordinator will monitor participants for adverse events and for adherence to the study protocols. We have developed the following medical alert and reporting policies:

### 1. ARES questionnaire

- a. Scores greater than or equal to six.
  - i. Send letter to participant and the participant's primary care provider, if available, referring the participant to a nearby sleep disorders center for further evaluation and treatment.

### 2. Depression

Depressive symptoms will be assessed using PHQ-9 during the screening interview. Individuals identified with moderate/severe or severe depression during the screening interview will not be enrolled in the intervention phase of the study as per study protocol. If moderate/severe or severe depression is identified, a medical alert and reporting policy has been developed along with a Depression Safety and Referral Plan (see Depression Safety and Referral Protocol and Arranging Care).

### a. PHQ-9 score ≥15

i During screening, the interviewer will proceed to assess the participant for thoughts of suicide using the Columbia-Suicide Severity Rating Scale, before continuing with other pre-screening surveys. The interviewer shall stay with the participant during this time and proceed with the response protocol for the Columbia-Suicide Severity Rating Scale based on the participant responses, as well The Depression Safety and Referral Protocol and Arranging Care.

Participant Screening and Enrollment. When individuals are contacted to determine their interest in participating in the study, no language will be used that will indicate any study opportunity/eligibility or personal health information unless research personnel are speaking directly with the party of interest. All data from participants screened for the study will be entered into the Research Electronic Data Capture (REDCap). The collected data will be helpful in examining the patient population and feasibility of enrollment criteria and will include gender, age, race, and reason for exclusion. For retained participants, the research staff will collect

Version Date: September 27, 2019

and enter required data (written informed consent and demographics) onto study data forms in REDCap. Individuals will be assigned a unique study ID number.

This study ID number will be linked to the participant name only. Only the PI and the research coordinator will have access to the linkage between the participant identity and the study identification number. This linking file will be password protected and stored on a secure NYU server separate from study data. This linking file will be destroyed at closure of the study, and the study will remain open with the IRB until these identifiers are destroyed. The unique study identification number will be used on all data forms, and no personal identifiers will be connected to the data. Paper records, such as the informed consent documents, will be kept in a locked file cabinet in a locked office. All data will be reported in aggregate.

Binders. The research coordinator will prepare and maintain a participant-specific binder for each participant containing all non-electronic Case Record Files. A regulatory file will also be maintained to include the IRB-approved protocol, original informed consent documents, and other study-related regulatory documents. All paper research records and case record files will be maintained in a locked file cabinet in a secure facility within the College of Nursing. Access to the research records, study database and PHI's will be restricted to study personnel as approved by the PI and IRB.

Data entry, processing, monitoring. This study will use REDCap for data capture and management. Data exports will be limited to the PI, the research coordinator, and the statistician for generating reports and conducting statistical data analysis. Weekly meetings will include reports on participant recruitment and retention, adverse events, and protocol deviations. Monthly meetings will consist of summaries of monthly accrual and cumulative accrual, key characteristics of the study participants, and the completeness and quality of data. Information on missing, invalid, and inconsistent data on selected key variables will be reviewed.

Data Security. All data will be saved in an electronic database on a secure NYU server. All system logins, data entries, and data updates are recorded, enabling efficient data tracking. Access to the server is available only to authorized users with passwords; overall data security is ensured by a firewall. Additional security is provided by database software requiring a password for data entry and allowing for password protection at the record level within a database. Patient confidentiality will be ensured by eliminating from the design of the data systems any information that could be used to identify individual participants. Each participant will be identified in the database only by a project-specific ID number. Identifiable information (e.g., name, birthdate, home address, or other personal information) will not be stored on any of the devices used in this study. For mobile devices and software such as the tablets or cell phones that will be used to gather survey data, guidelines established by NYU IRB will be followed including documentation of security controls, incident response program, compliance certifications, privacy practices, physical data security, and subcontractors. The packages that are shipped to and from study participants will not have any information on the exterior of the box indicating that they are a research participant.

**External factors.** The PI will monitor developments in the literature as the study progresses. Should it become clear that the intervention would be in any way harmful to participants, would increase risk, or would be unethical to continue, the IRB and study sponsor will be notified and the study will be stopped.

**Futility analysis.** As this pilot study is designed to determine acceptability and feasibility for a future well-powered R01 application, it will not be possible to determine whether the intervention is futile for this population during the proposed study.

# 11 Clinical Monitoring

Clinical site monitoring is conducted to ensure that the rights and well-being of human subjects are protected, that the reported trial data are accurate, complete, and verifiable, and that the conduct of the trial is in compliance with the currently approved protocol/amendment(s), with GCP, and with applicable regulatory requirement(s).

Version Date: September 27, 2019

Authorized representatives of the IRB and the NINR may review de-identified information, as well as participants' identifiable information, for the purposes of assuring proper conduct of the research, addressing a specific reported incident, or verifying appropriate use of funds. The Quality Assurance and Quality Improvement Division of NYU's Research and Regulatory Services may audit the study to confirm compliance. Access of any protected health information will be done in the offices of the PI in his presence. No identifiable information may be copied or taken off-site.

The project manager (or clinical research coordinator) will audit one case per quarter, selected at random, to confirm compliance with IRB requirements, including conformance with informed consent requirements, verification of source documents, and investigator compliance.

## 12 Statistical Considerations

## 12.1 Statistical and Analytical Plans

A formal SAP will be developed for this study in consultation with the study biostatistician. Only a general overview of study statistics is included in this protocol.

## 12.2 Statistical Hypotheses

The sample size is too small to make inferences about relationships evaluated in the pilot study to the larger population of middle aged adults with MetS. For the primary aim, acceptability will be evaluated by the percentage of participants rating SASI as acceptable (overall acceptability survey scores greater than 21), neutral (overall acceptability survey scores equal to 21), and unacceptable (overall acceptability survey scores less than 21) on the Acceptability Survey at each of two time points (pre-intervention and post intervention). Feasibility will be evaluated by the 1) recruitment rate: the percentage of potential participants screened in order to enroll 60 participants with evaluable data, 2) attrition rate: the percentage of enrolled participants completing the 18-week study. Participants will be considered withdrawn after 4 weeks of not responding to phone calls/emails during the intervention, and the 3) protocol adherence rates; the percentage of participants completing greater than or equal to 4 daily sleep diary entries per week for 80% or more of the intervention period. For the secondary endpoints, paired t-tests will be used to compare the mean preintervention and mean post-intervention estimates for SAFTEE scores, physical activity, sedentary behavior, diet quality, smoking, alcohol use, affective well-being, morning fatique, evening fatique, and self- regulation measurements. For the exploratory endpoints of perceived barriers and facilitators of SASI, bivariate correlations between specific socio-ecological factors and sleep duration change will be identified. The qualitative data from the post intervention interviews will be analyzed using content analysis. Content analysis includes a line- by-line review that yields clusters of data that are coded. This coding is linked to interview questions. Summarization of coding will be performed across individual interviews, and subsequently crossclassified to yield a rich descriptive analysis. Emerging themes within and across interviews will be identified, and review of fit with data verified.

## 12.3 Analysis Datasets

The analysis dataset will include all participant (e.g., intent to treat).

### 12.4 Description of Statistical Methods

### 12.4.1 General Approach

This is a 1-group pretest-posttest pilot study of the acceptability and feasibility of a sleep intervention.

Using descriptive analyses, the investigators will describe each variable using measures of central tendency (means, medians) and variability (standard deviations, interquartile ranges) for continuous variables; counts and percentages for categorical variables. Data will be evaluated for anomalies (e.g., nonrandom missing data, erroneous outliers, multicollinearity, possible confounding) that may invalidate planned analyses. Data transformations, imputation, and/or robust and tailored analysis approaches will be used for non-normally distributed variables.

Version Date: September 27, 2019

### 12.4.2 Analysis of the Primary Efficacy Endpoint(s)

For Aim 1: Acceptability will be based on the pre- and post-intervention acceptability survey measurements. The acceptability survey is an ordinal scale with higher scores indicating greater acceptability. Results will be reported as a categorical outcome indicating the count and percentage of participants rating SASI at the pre-intervention assessment as well as the post intervention assessment as acceptable (total scores greater than or equal to 21), neutral (total score equal to 21), and unacceptable (total scores less than 21).

Feasibility will be based on recruitment, retention, and study protocol adherence. Recruitment will be measured as the number and percentage of participants screened and their determination as eligible or ineligible based on inclusion/exclusion criteria. Results will be reported as a recruitment rate indicating the count and percentage of participants eligible and ineligible. Attrition rates will be reported as the number

and percentage of participants who withdraw from the study. Attrition rates >20% will suggest lack of feasibility. Recruitment and attrition rates will also be examined for differences in specific subgroups. Study protocol feasibility will be indicated by percentage of participants providing at least 4 work day sleep diaries per week for greater than or equal to 80% of the intervention period.

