Study Sites	NYU Langone Health NYU Rory Meyers College of Nursing

Version Date: September 27, 2019

	Bellevue Hospital [name] in C/D Building, 4th Floor New York, NY.

Drug/Device Template Version: 13 JUN 2016

Number of participants	We will screen approximately 220 individuals for a final sample of N= 60 participants. Of these 220 participants, we anticipate that 65% will become ineligible through the multi-stage screening process and 20% will be lost to attrition during the intervention leaving 60 participants with evaluable data.
Description of Study Intervention/Procedure	SASI is based on Cognitive Behavioral Therapy for Insomnia (CBTI). Like CBTI, SASI extends sleep based on sleep efficiency (the proportion of time spent sleeping during a sleep episode). Bedtimes and wake times will be prescribed each week for each participant and allow for gradual increases in sleep opportunity. Bedtimes will be set 15 minutes earlier each week provided sleep efficiency remains >90%. Earlier bedtimes will extend sleep duration by increasing the opportunity for sleep. Wake times will not be changed because wake times are often determined by external demands, such as work schedules.
Reference Therapy	Not applicable.
Key Procedures	Surveys, patient reported outcomes, anthropometric measurements, blood pressure measurement, daily sleep diaries, wrist accelerometry, blood draw (3 ml CTSI visit 1), open-ended interview.
Statistical Analysis	Primary endpoints: 1) Acceptability based on the percentage of pre and post intervention acceptability surveys with total scores < 21 (unacceptable), 21 (neutral), greater than 21 (acceptable). 2) Feasibility will be based on recruitment, retention, and study protocol adherence rates.

Version Date: September 27, 2019

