#### 3.2 Study Endpoints

#### 3.2.1 Primary Study Endpoints

This pilot study is designed to test the acceptability and feasibility of SASI. The primary endpoint, acceptability, will be evaluated by the percentage of participants rating SASI as acceptable (overall acceptability survey scores greater than 21), neutral (overall acceptability survey scores equal to 21), and unacceptable (overall acceptability survey scores less than 21) at each of two time points (pre- intervention and post intervention). The feasibility endpoints will be determined by the 1) recruitment rate: the percentage of potential participants screened in order to enroll 60 participants 2) attrition rate: the percentage of enrolled participants completing the 18-week study. Participants will be considered withdrawn after 4 weeks of not responding to phone calls/emails during the intervention and the 3) protocol adherence rates: the percentage of participants completing greater than or equal to 4 daily sleep diary entries per week for 80% or more of the intervention period.

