#### 7.3.3 Intermediate Visits

#### Week 1: Baseline Data Collection

- See Table 3 for study related procedures during week 1
- See Table 4 for baseline surveys to be completed during week 1 or 2.

Table 3: Baseline Data Collection	on Week 1		
	Number of times to complete per week	Number of questions	Estimated time
Wrist accelerometer and fitbit	Wear 24/7	n/a	n/a
Pulse oximeter (as needed per protocol)	Wear for 1 night	n/a	n/a
Daily sleep diary	7	9	< 5 minutes/day < 35 minutes/week
PROMIS Fatigue 6a -morning	1	6	< 5 minutes
PROMIS Fatigue 6a - evening	1	6	< 5 minutes
Epworth Sleepiness Scale	1	8	< 5 minutes/week
TOTAL TIME			< 50 minutes/week

Version Date: September 27, 2019

Table 4: Baseline Surveys Completed during Baseline Weeks 1 or 2			
	Number of questions	Estimated time	
Acceptability Survey (pre-intervention)	7	< 5 minutes	
Composite Scale of Morningness	13	5 minutes	
Economic Vulnerability Survey	8	5 minutes	
Family Assessment Device – General Functioning Scale	12	< 5 minutes	
Sleeping Environment Survey	11	5 minutes	
36-item Short Form Health Survey (SF- 36) version 1	36	40 minutes	
ASA24	varies	24 minutes	
Demographics – SDOH: Alcohol use (AUDIT C)	3	< 5 minutes	
Demographics – SDOH: Tobacco use	2	< 5 minutes	
Index of Self-Regulation	9	5 minutes	
SAFTEE	128	10 minutes	
PROMIS Depression 6a	6	< 5 minutes	
TOTAL TIME		~114 minutes	

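### Acceptability, a primary endpoint measured before and after SASI, is planned only as three category percentages around a total of 21, which can hide large within-person falls, and Section 12.4.2 lets two of the categories overlap

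*Combined protocol and SAP*

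**What the plan says.** Section 12.4.2 describes the instrument this way: "The acceptability survey is an ordinal scale with higher scores indicating greater acceptability". It then fixes the form of the result: "Results will be reported as a categorical outcome indicating the count and percentage of participants rating SASI at the pre-intervention assessment", and likewise after the intervention. Section 3.2.1 counts a participant as "rating SASI as acceptable (overall acceptability survey scores greater than 21" and as "neutral (overall acceptability survey scores equal to 21", with lower totals unacceptable, at each of the two time points. Section 12.2 uses the same three groups. The Protocol Summary gives "total scores < 21 (unacceptable), 21 (neutral), greater than 21 (acceptable".

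Section 12.4.2 words the groups differently: "acceptable (total scores greater than or equal to 21), neutral (total score equal to 21), and unacceptable (total scores less than 21".

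The survey has 7 questions at both times. Table 4 in Section 7.3.3 lists it as "Acceptability Survey (pre-intervention", and Table 10 in Section 7.4 lists the post-intervention administration. The scoring of each item and the range of the total are not stated.

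Section 12.4.1 promises means, medians, standard deviations and interquartile ranges for continuous variables, and counts with percentages for categorical ones. The paired t-tests in Sections 12.2 and 12.4.3 cover secondary endpoints and leave acceptability out.

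**The concern.** The survey is repeated after twelve weeks of SASI, so it can show whether acceptability holds up in use. The planned summary discards most of what it could tell. A participant just above the neutral total and one at the top of the scale are reported identically, and a participant who moves from the second position to the first is reported as unchanged. Because the two sets of percentages are unlinked, the report will not show who moved or in which direction.

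The pilot is meant to inform a randomized trial (Sections 1.1 and 1.2). No success threshold is set for acceptability, so readers will have only the category percentages to judge by. The overlapping definition in Section 12.4.2 adds a second problem: a total of exactly 21 belongs to two categories.

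**Working it through.** **1. The plan's own figure.** No target, precision or power is stated for acceptability. The only derived figure is the final sample in Sections 4 and 12.5: 220 screened, 65% ineligible, 20% attrition.

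220 × (1 − 0.65) = 77; 77 × (1 − 0.20) = 61.6, against the stated 60.

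The figure reproduces. The point does not depend on it, but it implies about 77 − 61.6 = 15.4 participants lost during the intervention.

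**2. What the categories hold.** Inputs: 7 items (Tables 4 and 10) and a neutral total of 21, so neutral is 21/7 = 3 per item. Two scorings put the midpoint at 21; both are assumptions. The cut-offs applied here are below, at and above 21.

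| Assumed item scoring | Range of total | Unacceptable | Neutral | Acceptable | Largest fall within acceptable |
|---|---|---|---|---|---|
| 1 to 5 | 7–35 (28 points) | 14 totals | 1 | 14 totals | 35 − 22 = 13; 13/28 = 46% |
| 0 to 6 | 0–42 (42 points) | 21 totals | 1 | 21 totals | 42 − 22 = 20; 20/42 = 48% |

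A total of 22 is 22/7 = 3.14 per item, against 3.00 for neutral. Under either scoring it is classed with the maximum.

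**3. Extreme case.** Under 1 to 5 scoring, suppose 60 participants all fall from 35 to 22. The planned report shows 60/60 (100%) acceptable at both times. The median within-person change is 22 − 35 = −13.

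**4. Less extreme illustration.** Assume roughly normal totals, truncated to 7–35, with the nominal mean falling from 31 to 27.

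| Nominal SD | Mean after truncation, pre → post | % above 21, pre → post | Movement in the reported figure |
|---|---|---|---|
| 2 | 30.9 → 27.0 | 100.0 → 99.7 | 0.3 points |
| 3 | 30.6 → 27.0 | 99.9 → 96.7 | 3.2 points |
| 4 | 30.0 → 26.8 | 99.0 → 91.4 | 7.6 points |

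The same loss of acceptability may barely register or may be visible, depending on a spread that the plan does not report.

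**5. Cancellation.** If k participants move from acceptable to unacceptable and k others move the opposite way, both percentages are unchanged for any k. Only a cross-table shows the 2k movers.

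**6. Who is compared.** Participants who withdraw have no further procedures (Section 7.5), and no new data are collected from them (Section 4.5.2). They contribute to the pre-intervention percentages but not to the post-intervention ones, so part of any difference can come from who left.

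**7. The overlap.** With acceptable at 21 or more and neutral at 21, a share p of participants at exactly 21 is counted twice, and the three percentages add to 100% + p. With acceptable above 21, as in the other three places, they add to 100%.

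**The case against.** Section 12.1 says that a formal SAP will follow and that the protocol gives only an overview, and Section 12.4.1 says each variable will be described. On that view, extra table rows are detail an overview may omit. Part of this stands: nothing forbids reporting the total score. But Section 12.4.1 assigns means and medians to continuous variables, and Section 12.4.2 declares this outcome categorical. Even a generous reading gives separate summaries at each time and never a within-person change.

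A second objection is that change is not the stated endpoint, and that Section 12.2 calls the sample too small for inference. That is fair, so the change belongs in the plan as description, with its interval as a statement of precision and not as a test.

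Third, a paired change omits those who withdrew, who may be the ones who liked SASI least. This stands. Pairing removes the mismatch between the two groups, but it does not recover the missing views.

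A reader might go further and infer that the categories cannot show erosion at all. The documents do not support that: any fall to 21 or below from above changes the reported percentages, and step 4 shows about 8 points of movement at an SD of 4. The final interview, retention and diary adherence also bear on how SASI is received.

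A reader might also infer that indifferent participants will be counted as accepting SASI. Someone neutral on every item totals 21 and is neutral under the definition used in three of the four places. Scattered answers around neutral would fall below 21 about as often as above it, and the plan reports that share too.

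**Conclusion.** The concern holds as a loss of information in a descriptive primary endpoint, together with a direct contradiction in its cut-off. No test, error rate, power figure or decision rule is affected.

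The collapse of all totals above 21 into one category, the cancellation of opposite moves, and the absence of any planned paired summary follow from the text alone. The size rests on unstated item scoring: up to 13 of 28 points can be hidden under 1 to 5, or 20 of 42 under 0 to 6, which is just under half the scale either way. A maximum of 35 should not be read as a documented fact. The movements of 0.3 to 8 percentage points rest on an assumed score shape and spread.

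The overlap at 21 needs no assumption. Section 12.4.2 disagrees with the Protocol Summary, Section 3.2.1 and Section 12.2, and must be reconciled with them.

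**What to change.** In Section 12.4.2:

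- Reconcile the cut-off so that the categories do not overlap: above 21, exactly 21 and below 21, as in the other three places. Keep the three categories.
- State the item scoring and the possible range of the total.
- Add the median (IQR) and mean (SD) total score at each time point.
- Add the within-person post-minus-pre change with a 95% CI, labelled descriptive, in participants with both surveys.
- Add a pre-by-post cross-table of the three categories, with a row for participants whose post-intervention survey is missing.
- State that the paired results exclude withdrawn participants, and give the number excluded.

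The cost is a few table rows. No new data, visits or participants are needed. The remaining limitation is that the change estimate describes only participants with both surveys.

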## 4 Study Enrollment and Withdrawal

To reach a final sample of N= 60, we will recruit 220 individuals. Of these, we anticipate that 65% will become ineligible through the multi-stage screening process and 20% will be lost to attrition during the intervention leaving 60 participants with evaluable data.

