#### 7.4 Final Study Visit (within 3 weeks of completing SASI): Duration < 60minutes

- Record any new medications prescribed during the study period to treat hyperglycemia, hypertension, hypertriglyceridemia, or low HDL-c.
- See Table 10 for study related procedures.
- Record adverse events as reported by participant or observed by investigator.
- Notify participant that aggregate-level results will be available after dissemination of study findings begins.
- Instruct participant to report any subsequent event(s) that the participant, or the participant's
  physician, believes might reasonably be related to participation in this study.

Table 10: Final Study Visit (at home)		
	Number of questions	Estimated time
Acceptability survey (post intervention)	7	< 5 minutes

Version Date: September 27, 2019

Open ended interview	varies	30 minutes
TOTAL TIME		~ 35 minutes

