### 12.4.6 Baseline Descriptive Statistics

Baseline characteristics, including demographic and clinical characteristics of the sample, using descriptive statistics will be compared between participants for whom the intervention was acceptable and for whom the intervention was unacceptable at each time point (pre-intervention and post- intervention). Inferential statistics will not be used.

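### Section 12.4.2 places an acceptability score of exactly 21 in two categories, against the exclusive rule in the three other places that define this primary endpoint

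*Combined protocol and SAP*

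**What the plan says.** Four places in the combined document set the cut-offs for the acceptability survey.

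- Protocol Summary, Statistical Analysis row: "Acceptability based on the percentage of pre and post intervention acceptability surveys with total scores < 21 (unacceptable), 21 (neutral), greater than 21 (acceptable".
- Section 3.2.1 (Primary Study Endpoints): "overall acceptability survey scores greater than 21), neutral (overall acceptability survey scores equal to 21", with scores below 21 unacceptable.
- Section 12.2 (Statistical Hypotheses): "the percentage of participants rating SASI as acceptable (overall acceptability survey scores greater than 21", again with 21 neutral and below 21 unacceptable.
- Section 12.4.2 (Analysis of the Primary Efficacy Endpoint(s)): "acceptable (total scores greater than or equal to 21), neutral (total score equal to 21), and unacceptable (total scores less than 21".

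Section 12.4.2 describes the result as one categorical outcome, given as counts and percentages before and after the intervention. Section 12.4.6 then uses the classification to form groups: baseline characteristics are "compared between participants for whom the intervention was acceptable and for whom the intervention was unacceptable at each time point", without inferential statistics.

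The survey has 7 questions (Table 4 in section 7.3.3 and Table 10 in section 7.4). It is given once in baseline weeks 1 or 2 and once at the final visit. Section 12.1 says that a formal SAP will follow and that the protocol gives only an overview.

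**The concern.** A categorical outcome needs categories that do not overlap. In 12.4.2 they overlap at 21, the one score that the plan names as a category of its own. Someone who applies that section as written counts a neutral respondent as acceptable as well. The error can run only one way, towards a more favourable acceptable percentage.

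Two outputs are exposed. The first is the primary table of acceptable, neutral and unacceptable at each time point. The second is the descriptive comparison in 12.4.6. Under 12.4.2 a person scoring 21 could be placed in its acceptable group; under the other three definitions that person belongs to neither group compared. Because 12.4.2 is the section that an author of the formal SAP would naturally work from, the slip could be carried forward.

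**Working it through.** **Step 1. The two rules side by side.**

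| Total score | Section 12.4.2 | Summary, 3.2.1 and 12.2 |
|---|---|---|
| below 21 | unacceptable | unacceptable |
| exactly 21 | acceptable and neutral | neutral |
| above 21 | acceptable | acceptable |

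Classifying every whole-number score from 0 to 59 under both rules confirms this. Under 12.4.2, 21 is the only score with two labels and no score lacks a label. Under the other rule there is no overlap and no gap. The rules disagree at 21 and nowhere else.

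**Step 2. Effect on the percentages.** Among N respondents at one time point, let a score above 21, k score exactly 21 and u score below 21, so that N = a + k + u.

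- Acceptable under 12.4.2: (a + k)/N. Acceptable under the other rule: a/N. Difference: k/N.
- Sum of the three categories under 12.4.2: (a + k + k + u)/N = 1 + k/N.
- Sum under the other rule: (a + k + u)/N = 1.

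The overstatement and the excess over 100% are the same quantity, the share scoring exactly 21. Both are zero when k = 0.

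**Step 3. The base at each time point.** Section 4 plans 220 people, 65% becoming ineligible during screening and 20% lost during the intervention, "leaving 60 participants with evaluable data". The plan's figure is reproduced to rounding: 220 × 0.35 = 77, and 77 × 0.80 = 61.6, against a stated 60.

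- After the intervention: the survey is taken at the final visit, and section 7.5 ends all procedures on withdrawal, so the base is about 60. One person is 1/60 = 1.7 points (1/62 = 1.6 if 61.6 is rounded up).
- Before the intervention: the survey is taken in weeks 1 or 2, before the week 3 eligibility check (7.3.3.3) and before attrition. With full response the planned base is at least 77, so one person is at most 1/77 = 1.3 points.

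**Step 4. Illustration.** The documents give no count at 21, so k is assumed.

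| Assumed k | Overstatement, N = 60 (post) | Sum | Overstatement, N = 77 (pre, upper limit) | Sum |
|---|---|---|---|---|
| 0 | 0 | 100% | 0 | 100% |
| 3 | 5.0 points | 105.0% | 3.9 points | 103.9% |
| 6 | 10.0 points | 110.0% | 7.8 points | 107.8% |
| 9 | 15.0 points | 115.0% | 11.7 points | 111.7% |

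**Step 5. Which wording is out of line.** Three places agree with one another against 12.4.2. Section 12.4.2 also keeps a neutral category at 21, and under its own definition of acceptable that category has no members of its own. Removing the equality from acceptable restores one category per score.

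**The case against.** The strongest reply is that the document already settles the matter. The endpoint definition in 3.2.1 is exclusive and two other places repeat it. Section 12.4.2 calls the outcome categorical and gives 21 its own label. A careful analyst would notice and use 3.2.1. The statistical section is described as an overview with a formal SAP to follow. On this view it is an editorial slip. That stands as an argument about weight. It does not remove the contradiction, which is in current text and sets the cut-off of a primary endpoint.

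A reader might also infer more than the documents support:

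- **That the percentages must exceed 100%.** They do so only if at least one respondent scores exactly 21, and nothing in the plan says how likely that is. The average at 21 is 21/7 = 3 per item, but the response scale is not stated. If items ran 1 to 5, totals would run 7 to 35 and 21 would be the midpoint; if 1 to 4, totals would run 7 to 28 with midpoint 17.5. The contradiction does not depend on either assumption.
- **That 1.7 points per person applies at both time points.** It fits only the post-intervention survey; the earlier survey has a larger planned base.
- **That respondent numbers go unreported, or that the pre and post percentages will be read as change.** Section 12.4.2 already asks for counts with percentages, and exclusive counts add up to the number of respondents. Acceptability is not among the pre/post comparisons in sections 2, 2.2 or 12.4.3.

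**Conclusion.** The inconsistency is real and confined to one score. Its size is the share of respondents scoring exactly 21, which is unknown and may be zero. The per-person figures rest on the planned screening and attrition rates, and the pre-intervention one also on full response.

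It would be tempting to conclude that the slip could change whether the intervention is declared acceptable. The documents do not support that. They set no success threshold for acceptability and no test, the sample size does not derive from it, and 12.4.6 excludes inferential statistics. The only study-level cut-off in 12.4.2 is attrition above 20%, which does not use the survey. Severity is minor: a correction to the text, with no threat to the trial.

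**What to change.** In section 12.4.2, define acceptable as a total score greater than 21, leaving neutral at exactly 21 and unacceptable below 21. That brings it into line with the Protocol Summary, 3.2.1 and 12.2. Have 12.4.6 refer to the same three exclusive categories, so that a score of 21 falls in neither the acceptable nor the unacceptable group, and carry the wording into the formal SAP.

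The cost is one phrase in 12.4.2 and a cross-reference in 12.4.6, with no new data, visits or participants. The only effect on results is that the acceptable percentage is lower than under the literal 12.4.2 reading by the share scoring exactly 21.
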